4. GENERAL CONSIDERATIONS FOR DATA ANALYSIS

Unless otherwise specified, continuous variables will be summarized using descriptive statistics (n, mean, standard deviation, median, minimum, and maximum). Categorical variables will be summarized showing the number and percentage of subjects within each category.

Summary results will be provided for each treatment group. All tabulations will be based on pooled data across centers.

Unscheduled visits will be excluded from the summaries but will be included in the data listings.

All statistical tests will be two-sided and tested at the 10% level of significance.

Analyses will be performed using SAS for Windows statistical software, version 9.4 or higher (SAS, Cary, NC), except where other software may be deemed more appropriate.

CTI will perform all efficacy and safety analyses described in this SAP.

Subject data will be listed, sorted by treatment group and subject number. When applicable, listings will be additionally sorted by visit and assessment date/time.

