4.5 Multiple Comparisons

Because of the exploratory nature of this study, there will be no adjustment for multiple comparisons.

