From this model, the least-squares (LS) means and 90% CIs for each treatment group, the treatment difference in the LS means, the 90% CI for the difference, and the associated p-value will be presented.

If the data cannot support ANCOVA model assumption, a sensitivity analysis will be performed using proportional-odds cumulative logit model. The cumulative logits model will compare lower ordinal scales to higher ones, or equivalently, more favorable outcomes to less favorable ones. The model may be adjusted for baseline characteristics such as age, if appropriate. The estimated odds ratio and 95% CI will be presented.

The proportional odds assumption will be tested using a score test at the two-sided alpha level of 0.05. In the event that the proportional odds assumption is not satisfied, given the anti-conservative nature of the score test, the proportional odds model will still be used for the analysis, and the results will be presented along with the score test p-value to help put these results in context. If the proportion odds assumption is rejected or if the proportional odds model fails to converge, an alternative analysis using Cochran-Mantel-Haenszel (CMH) test will be performed to evaluate the association between the treatment groups and the maximum change in ordinal scale from baseline. The p-value for CMH row mean scores statistic will be reported.

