6.2 Secondary Efficacy Endpoints and Analyses

Incidence of SARS-CoV-2 infection through Day 29

The analysis of the proportion of subjects who had a positive result from the SARS-CoV-2 test within 28 days from the first dose of study drug will be performed using the mITT set.

The null hypothesis is that there is no difference in proportions of subjects with SARS-CoV-2 infection through Day 29 between randomized treatment groups; H₀: $\pi_t - \pi_c = 0$. The alternative hypothesis is that the proportions of subjects with SARS-CoV-2 infection through Day 29 are different between the treatment groups; H₁: $\pi_t - \pi_c \neq 0$.

The proportion of mITT subjects with SARS-CoV-2 infection within each treatment group will be presented along with a two-sided exact (Clopper-Pearson) 90% confidence interval (CI).

The observed difference in the proportion of subjects with SARS-CoV-2 infection between treatment groups along with the exact unconditional 90% CI for risk difference will be calculated. The null hypothesis will be tested using Fisher's exact method and the p-value will be reported.

Incidence of SARS-CoV-2 infection through Day 15

The analysis of the proportion of mITT subjects who had a positive result from SARS-CoV-2 test within 14 days from the first dose of study drug will be performed using the method described above for the analysis of incidence of SARS-CoV-2 infection through Day 29.

Severity of COVID-19 through Day 15

The change in severity of COVID-19 from baseline through Day 15 between the treatment groups will be compared using an ANCOVA model, including the maximum change in Ordinal scale from baseline through Day 15 as a dependent variable, treatment group as a fixed effect, and baseline

characteristics such as age as a covariate.

From this model, the least-squares (LS) means and 90% CIs for each treatment group, the treatment difference in the LS means, the 90% CI for the difference, and the associated p-value will be presented.

If the data cannot support ANCOVA model assumption, a sensitivity analysis will be performed using proportional-odds cumulative logit model as described above for the primary efficacy endpoint analysis.

Ordinal Scale through Day 29

The absolute value and change from baseline in the Ordinal scale from Day 1 through Day 29 will be summarized by treatment group and visit using descriptive statistics.

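### The proportional-odds odds ratio for the primary endpoint gets a 95% CI, while tests are at two-sided 10% and every other stated efficacy interval is 90%; no reason is given

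*SAP*

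**What the plan says.** SAP section 4 sets the level for the whole plan: "All statistical tests will be two-sided and tested at the 10% level of significance". For the primary ANCOVA, section 6.1 follows it and promises "the treatment difference in the LS means, the 90% CI for the difference, and the associated p-value will be presented".

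Section 6.1 then adds a second model: "If the data cannot support ANCOVA model assumption, a sensitivity analysis will be performed using proportional-odds cumulative logit model". Its treatment result is specified in one sentence: "The estimated odds ratio and 95% CI will be presented".

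The other stated efficacy intervals are all 90%:
- ANCOVA least-squares means and differences at Day 29 and Day 15 (6.1, 6.2)
- infection proportions and risk differences (6.2)
- ICU admission and mechanical ventilation, with ventilation referring back to the ICU method (6.2)
- ICU days and ventilation days (6.2)
- mortality and Kaplan-Meier estimates (6.2)

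The symptom-score Wilcoxon tests in 6.2 use a two-sided alpha of 0.1.

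Two later analyses point back to this model. The Day 15 severity sensitivity analysis is done "using proportional-odds cumulative logit model as described above for the primary efficacy endpoint analysis", and the subgroup analyses in 6.3 use the method of 6.1. Section 13 of the protocol states neither a test level nor a confidence level.

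**The concern.** A sensitivity analysis of the primary endpoint should show whether the ANCOVA conclusion survives a change of model. Here the model and the confidence level change together. The odds-ratio interval will be read beside an ANCOVA interval and p-value on the 10% standard. If the first includes 1 and the second excludes 0, a reader cannot tell at a glance whether the models disagree or whether one interval is simply wider by design.

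Nothing in the plan explains the exception. The nearest 0.05 is in "The proportional odds assumption will be tested using a score test at the two-sided alpha level of 0.05", but that is a diagnostic of the model and not a comparison of treatments. Multiplicity does not explain it either: "Because of the exploratory nature of this study, there will be no adjustment for multiple comparisons". A one-sided reading does not help, because a one-sided 5% test pairs with a two-sided 90% interval, and section 4 says the tests are two-sided.

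**Working it through.** **Level implied by the plan.** Two-sided alpha is 0.10 (SAP 4), so the matching interval is 1 - 0.10 = 90%. This reproduces every other stated efficacy interval. It does not reproduce 95%, which pairs with alpha 0.05.

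**Width.** The multipliers are 1.960 (95%) and 1.645 (90%). The ratio is 1.960/1.645 = 1.19 on the log-odds scale; the reverse is 1.645/1.960 = 0.84.

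**Worked example.** The planned size is 100 per arm (SAP 9). The counts are assumed: 11 infected on PUL-042 and 20 on placebo, all with a maximum score of 1, without covariates.

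- Mean difference: 0.11 - 0.20 = -0.09.
- Pooled variance: (100 × 0.11 × 0.89/99 + 100 × 0.20 × 0.80/99)/2 = (0.0989 + 0.1616)/2 = 0.1303.
- SE: √(0.1303 × 2/100) = 0.0510; t = 0.09/0.0510 = 1.76, p = 0.08. The 90% CI is **-0.174 to -0.006**.
- Log odds ratio: ln[(11/89)/(20/80)] = ln 0.494 = -0.704. SE: √(1/11 + 1/89 + 1/20 + 1/80) = 0.406.
- Odds ratio 0.49. 95% CI: exp(-0.704 ± 1.960 × 0.406) = **0.22 to 1.10**. 90% CI: exp(-0.704 ± 1.645 × 0.406) = **0.25 to 0.96**.

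The same data give an ANCOVA-type interval that excludes 0 and a printed odds-ratio interval that includes 1. At 90% the two agree.

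**How often.** The quantity of interest is the share of trials in which ANCOVA is significant at 10%, the 95% odds-ratio interval includes 1, and the 90% interval excludes 1. This isolates the confidence level from genuine disagreement between the models. SAP 9 says infection rates are unknown, so the inputs are assumptions:
- 2000 simulated trials per scenario, 100 per arm
- treatment and age in both models; age effect on infection 0.3 log-odds per SD
- severity among the infected, scores 1 to 8: mix A 45/35/8/6/3/1/0.5/1.5%, mix B 60/35/3/2/0/0/0/0%, the same in both arms

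| Infection rate, placebo / PUL-042 | Mix A | Mix B |
|---|---|---|
| 5% / 2.5% | 6.0% | 6.8% |
| 10% / 5% | 7.3% | 8.3% |
| 15% / 7.5% | 5.9% | 7.3% |
| 20% / 10% | 5.6% | 5.9% |
| 30% / 15% | 2.9% | 5.1% |
| 40% / 20% | 1.8% | 1.7% |
| 20% / 20% | 2.4% | 3.1% |
| 10% / 10% | 2.2% | 3.5% |

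The range is 1.7-8.3% with infection halved and 2.2-3.5% with no effect. Monte Carlo SE is at most about 0.7 points. Fits that could not be estimated are excluded: 8% of trials at the 5% rate, under 1% elsewhere. Without age adjustment the range over the same scenarios is 1.7-8.1%.

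**Does the condition for the second model matter?** The SAP gives no formal trigger. With a Shapiro-Wilk test at 0.05 on the ANCOVA residuals as an assumed trigger, every estimable trial met it, so conditioning on it leaves these shares unchanged.

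**The case against.** Four points can be made for leaving the text alone.

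- Section 4 fixes the level of tests, not of intervals, and the plan nowhere says that significance is read from whether this interval includes 1. If a treatment p-value from the model is also printed, section 4 already judges it at 10%. This stands. A reader might infer that the SAP breaks its own rule; it does not.
- A 95% interval is a common convention and is the more cautious choice, and a reader can recover the 90% interval by multiplying the log-odds half-width by 0.84. This also stands, and it keeps the point small. It does not tell the reader whether 95% was intended.
- The example lies in the narrow band where p is between 0.05 and 0.10. It shows that a conflict is possible, not that it is typical. The shares above rest on assumed inputs. Some disagreement would also remain at 90%: 0.4-6.6% of trials at 100 per arm in the same simulation. That part is model disagreement and lies outside this point.
- A reader might extend the point to the Cochran-Mantel-Haenszel result, since "The p-value for CMH row mean scores statistic will be reported". The documents do not support that. Section 6.1 runs this test only if proportional odds is rejected or the model does not converge, and without convergence there is no odds-ratio interval to compare. In the all-score-1 example the outcome is binary, so there is no proportional-odds assumption to reject and the test would not be reported. In the scenarios above (run without age adjustment), the score test rejected in 2.4-7.3% of trials, and a level-driven conflict with this test arose in only 0.0-0.2%.

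**Conclusion.** The inconsistency is real and can be checked from the SAP text alone: one efficacy interval is specified at 95%, all the others stated are at 90%, and no reason is given. It reaches the Day 15 severity analysis, and any subgroup analysis using this model, by cross-reference.

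The consequence is minor. The level alone would make the odds-ratio interval look at odds with the ANCOVA in roughly 2-8% of trials at 100 per arm, given the assumed infection rates, severity mixes and age effect. The analysis is a conditional sensitivity analysis in a study that calls itself exploratory, and the error is in the conservative direction. A reader might infer that the primary conclusion is affected; it is not, because the primary ANCOVA, its p-value and its 90% interval are unchanged.

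**What to change.** In SAP section 6.1, change the confidence level of the proportional-odds odds ratio from 95% to 90%. Sections 6.2 (Day 15 severity) and 6.3 (subgroups) then follow by cross-reference without further edits. If 95% is deliberate, present the 90% interval as well and state why the second level is wanted.

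The cost is one number, or one sentence, and no extra analysis. The downside is a slightly less cautious odds-ratio interval.

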6.2 Secondary Efficacy Endpoints and Analyses

Incidence of SARS-CoV-2 infection through Day 29

The analysis of the proportion of subjects who had a positive result from the SARS-CoV-2 test within 28 days from the first dose of study drug will be performed using the mITT set.

The null hypothesis is that there is no difference in proportions of subjects with SARS-CoV-2 infection through Day 29 between randomized treatment groups; H₀: $\pi_t - \pi_c = 0$. The alternative hypothesis is that the proportions of subjects with SARS-CoV-2 infection through Day 29 are different between the treatment groups; H₁: $\pi_t - \pi_c \neq 0$.

The proportion of mITT subjects with SARS-CoV-2 infection within each treatment group will be presented along with a two-sided exact (Clopper-Pearson) 90% confidence interval (CI).

The observed difference in the proportion of subjects with SARS-CoV-2 infection between treatment groups along with the exact unconditional 90% CI for risk difference will be calculated. The null hypothesis will be tested using Fisher's exact method and the p-value will be reported.

Incidence of SARS-CoV-2 infection through Day 15

The analysis of the proportion of mITT subjects who had a positive result from SARS-CoV-2 test within 14 days from the first dose of study drug will be performed using the method described above for the analysis of incidence of SARS-CoV-2 infection through Day 29.

Severity of COVID-19 through Day 15

The change in severity of COVID-19 from baseline through Day 15 between the treatment groups will be compared using an ANCOVA model, including the maximum change in Ordinal scale from baseline through Day 15 as a dependent variable, treatment group as a fixed effect, and baseline

characteristics such as age as a covariate.

From this model, the least-squares (LS) means and 90% CIs for each treatment group, the treatment difference in the LS means, the 90% CI for the difference, and the associated p-value will be presented.

If the data cannot support ANCOVA model assumption, a sensitivity analysis will be performed using proportional-odds cumulative logit model as described above for the primary efficacy endpoint analysis.

Ordinal Scale through Day 29

The absolute value and change from baseline in the Ordinal scale from Day 1 through Day 29 will be summarized by treatment group and visit using descriptive statistics.

The number and percentages of subjects in each severity category of the 9-point Ordinal Scale will be presented by visit and treatment group.

Graphical illustrations of the Ordinal Scales through Day 29 will be presented using stacked bar chart for each treatment group. The X axis representing time points and Y axis representing the cumulative number of subjects for each Ordinal Scale. Each bar is divided into a number of subbars stacked end to end corresponding to different Ordinal Scales.

The changes in Ordinal Scales through Day 29 will be examined using box and whisker plots for each treatment group. The X axis representing the post-baseline time points and the Y axis representing the change from baseline in Ordinal Scales at each post-baseline visit.

Symptom Score

The symptoms due to SARS-CoV-2 infection will be assessed and the symptom scores (Cough (0-3), Shortness of breath or difficulty breathing (0-3), Muscle aches or fatigue (0-3), Fever (0-4)) will be recorded in the eCRF.

The respiratory symptom score will be calculated by summing the symptom scores from Cough and Shortness of breath or difficulty breathing. The total symptom score will be calculated by summing all symptom scores.

The scores from each symptom together with calculated respiratory symptom scores and total symptom scores will be summarized by presenting the number and percentage of ITT subjects for each category by visit and treatment group.

Each symptom score (Cough, Shortness of breath or difficulty breathing, Fatigue, Fever, Respiratory, Total) from each post-baseline timepoint will be compared between treatment groups using non-parametric Wilcoxon Rank Sum test at 2-sided alpha level of 0.1. The p-value will be presented at each post-baseline visit.

A radar plot will be created by presenting each symptom score in group mean at each time point by treatment group.

Subjects requiring ICU admission

Subject data pertaining to ICU admission will be recorded in the database.

The proportion of ITT subjects who are admitted to the ICU from Day 1 to Day 29 within each

treatment group will be presented along with a two-sided exact (Clopper-Pearson) 90% confidence interval (CI).

The observed difference in the proportion of subjects requiring ICU admission between treatment groups along with the exact unconditional 90% CI for risk difference will be calculated. The null hypothesis will be tested using Fisher's exact method and the p-value will be reported.

Subjects who have died without ICU admission during the study will be counted as requiring ICU admission for the analysis.

Number of ICU Days

The number of ICU days from Day 1 to Day 29 will be calculated based on the ICU admission and discharge dates recorded in the eCRF. The calculated number of ICU days will be compared between treatment groups using 2-sided Student's t-test. The 90% CI and p-value will be presented.

If the Student's t-test normality assumption is found to be clearly violated, a sensitivity analysis will be performed using a non-parametric Wilcoxon rank-sum test. The p-value from the test will be presented.

Subjects who died will be assigned as hospitalized in the ICU for the number of days remaining from the day of death to Day 29 for the analysis. Subjects who are alive and never admitted into the ICU will be included in the analysis with a value of zero ICU days.

Subjects who were at ICU at study completion will be assigned an ICU end date equal to the date of completion for the purpose of deriving number of ICU days.

Subjects requiring mechanical ventilation

Subject data pertaining to mechanical ventilation use will be recorded in the database.

The proportion of ITT subjects who were on mechanical ventilation from Day 1 to Day 29 within each treatment group will be analyzed and compared using the method described above for the analysis of subjects requiring ICU admission.

Subjects who have died without mechanical ventilation during the study will be counted as requiring mechanical ventilation for the analysis.

Number of days on mechanical ventilation

The number of days on mechanical ventilation from Day 1 through Day 29 will be calculated based on the start/stop dates of mechanical ventilation recorded in the eCRF. Number of days on mechanical ventilation will be compared between treatment groups using 2-sided Student's t-test. The 90% CI and p-value will be presented.

If the Student's t-test normality assumption is found to be clearly violated, a sensitivity analysis will be performed using a non-parametric Wilcoxon rank-sum test. The p-value from the test will be presented.

Subjects who died will be assigned as being on mechanical ventilation for the number of days remaining to Day 29 for the analysis. Subjects who had mechanical ventilation ongoing at study completion will be assigned a mechanical ventilation end date equal to the date of study completion for the purpose of deriving duration of mechanical ventilation. Subjects who are alive and never

CONFIDENTIAL

placed on mechanical ventilation will be included in the analysis with a value of zero days on mechanical ventilation.

Mortality Rate through Day 29

Subject status (Alive/Death) will be recorded in the database. If the vital status of the subject is missing at the end of the study, then the subject will be excluded from the binomial analysis for the mortality rate. The subject will be included in the Kaplan-Meier (KM) analysis with right censoring at the date the subject was last known to be alive.

The mortality rate (proportion of ITT subjects who die) through Day 29 within each treatment group will be presented along with a two-sided exact (Clopper-Pearson) 90% confidence interval (CI).

The observed difference in the mortality rate between treatment groups along with the exact unconditional 90% CI for risk difference will be calculated. The null hypothesis will be tested using Fisher's exact method and the p-value will be reported.

If deemed appropriate, an alternative analysis will be performed in which the survival rates will be estimated using the KM method. The KM estimates along with 90% CIs and survival curves will be provided. Based on the KM estimates, the survival probabilities and associated 90% CIs on Days 15 and 29 will be reported; in addition, the 25%, 50% (median), and 75% percentiles of the survival time with associated 90% CIs will be provided, as data permit. The survival rates between treatment groups will be compared using Log-rank test and the p-value from Log-rank test will be presented.

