8.2. SARS-CoV-2 Infection Assessment

Ordinal Scale for Clinical Improvement: A nine point scale will be used to assess the severity of COVID-19 which has been derived from the draft scale proposed by WHO.⁹

The following table will be used to assess symptoms due to SARS-CoV-2 infection:

Table 2: SARS-CoV-2 Infection Symptom Score

Symptom	Score (0-3)
Cough	
Shortness of breath or difficulty breathing	
Muscle aches or fatigue	
	Score (0-4)
Fever	

Symptom Scores (Cough, Shortness of breath or difficulty breathing, Muscle aches or fatigue)

- 0- None
- 1- Mild (occasional or not bothersome)
- 2- Moderate (frequent or bothersome)
- 3- Severe (interferes with daily activities)

Note: Fever will be scored based on temperature recorded as part of vital signs and graded according to the Toxicity Grading Scale for Healthy Adult and Adolescent Volunteers Enrolled in Preventive Vaccine Clinical Trials:

٠	0	No Fever
٠	1- Mild	38.0-38.4°C/100.4-101.1°F
•	2-Moderate	38.5-38.9°C/101.2-102.0°F
•	3-Severe	39.0-40.0°C/102.1-104.0°F

• 4-Life Threatening $> 40.0^{\circ}C/>104.0^{\circ}F$

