4.4 Handling of Dropouts or Missing Data

Except for the time to event endpoint (Table 1), partial end dates of prior and concomitant medications (Section 5.6), and partial onset dates of AEs (Section 7.2.1), all other missing data will be treated as missing and no method for imputation is planned.

Missing data on the time to event endpoint will have events coded as right censored per the following table:

Table 1 Missing Data Coding for Time to Event Data Analysis

Endpoint	Right Censoring
Subject Survival	Subjects who are still alive as of the last known follow-up will be
	right censored as of the date of last subject contact when the subject
	was known to be alive.

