11. APPENDIX

11.1 Appendix A: Schedule of Events

Event	Screening	Dose 1ª	Dose 2, 3, 4 ª	Follow-up/Early Discontinuation from Study	Study Completion
	Vl	V2	V3, 4, 5	V6	V 7
	Day -2 to Day 1	Day 1 ^b	Days 3, 6, 10	Day 15	Day 29
Informed consent	Х				
Medical history	Х				
Pregnancy test ^c	X			Х	Х
Physical exam	Х	X	Х	Х	
Vital signs ^d	Х	Х	Х	Х	
Spirometry ^e	Х	X	X		
Symptom score ^f	Х	Х	Х	X	Х
SARS-CoV-2 test ^g		Х		Х	х
Study drug administrationh		X	Х		
Adverse events	Х	Х	Х	Х	Х
Concomitant medications	X	X	Х	Х	Х
Ordinal Scale for Clinical Improvement	x	Х	Х	x	Х
Randomization	X				

^a Vital signs, adverse events, and concomitant medications will be assessed prior to administration of study medication and also at 30 minutes post-dose.

^b There is no Day 0 in this study

^c Urine pregnancy test or serum pregnancy test if women are of child-bearing potential. If urine pregnancy test is positive, a serum pregnancy test must be done. Pregnancy test is required for Early Discontinuation, not Day 15.

d Vital signs will include body temperature, blood pressure measurements, heart rate, and respiratory rate.

^e Spirometry will be done at screening to document eligibility. On days of dosing, spirometry will be done pre-dose and at 30 minutes (±15) minutes post-dose. If the FEV1 is reduced > 10% compared to the pre-dose baseline the FEV1 should be repeated as clinically indicated

f SARS-CoV-2 symptoms will be assessed at each visit according to the Symptom Score

^g SARS-CoV-2 testing will be performed pre-dose on Day 1 (Visit 2), Day 15 (Visit 6) and at Day 29 (Visit 7). Additional testing should be conducted at any point during the study when clinical symptoms are suggestive of potential COVID-19.

^h Study drug administration must be done by a health care professional

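### The visit-by-visit symptom-score tests drop subjects who have died, so they compare survivors only and can look neutral or even favour the arm with more deaths

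*SAP*

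**What the plan says.** SAP 2.2.2 lists the symptom score as a secondary efficacy endpoint. SAP 6.2 (Symptom Score) takes cough, shortness of breath, fatigue, fever, a respiratory sum and a total. Each is "compared between treatment groups using non-parametric Wilcoxon Rank Sum test at 2-sided alpha level of 0.1", and "The p-value will be presented at each post-baseline visit". The schedule in SAP Appendix A adds that "SARS-CoV-2 symptoms will be assessed at each visit according to the Symptom Score". The post-baseline visits are Days 3, 6, 10, 15 and 29.

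Nothing in that part of SAP 6.2 says what happens to a subject who has died. The general rule in SAP 4.4 therefore applies. Apart from the survival endpoint, partial medication end dates and partial adverse-event onset dates, "all other missing data will be treated as missing and no method for imputation is planned". The symptom scale offers no place for death: in Protocol 8.2 the cough, breathing and fatigue items stop at "3- Severe (interferes with daily activities"), and fever stops at a temperature grade of 4.

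Elsewhere in SAP 6.2 death does have a rule:

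- ICU admission: "Subjects who have died without ICU admission during the study will be counted as requiring ICU admission for the analysis".
- ICU days: "Subjects who died will be assigned as hospitalized in the ICU for the number of days remaining", up to Day 29.
- Mechanical ventilation: a death without ventilation is counted as requiring it.
- Ventilation days: "Subjects who died will be assigned as being on mechanical ventilation for the number of days remaining to Day 29 for the analysis".

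**The concern.** A subject who dies has no symptom score afterwards and leaves each later comparison because of the worst possible outcome. What remains is a comparison of survivors, a group formed after randomisation and possibly by the treatment itself. If one arm loses more subjects to death, its remaining scores can look the same as the other arm's. If the subjects who die were also the most symptomatic, its scores can look better.

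The SAP handles this for four neighbouring secondary endpoints, so its absence here reads as an omission. At stake is how the symptom-score p-values are read: a neutral or favourable result could be taken as evidence about symptoms in all treated subjects when it describes only those alive to be scored.

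**Working it through.** The documents give no power or expected result for these tests, so there is no planned figure to reproduce. The check compares two treatments of death: dropped (as planned) and ranked worse than any live score.

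**Inputs from the documents.** 100 per arm (SAP 9); Wilcoxon rank-sum, two-sided 0.10 (SAP 6.2); mortality of 5% and 15%, which are stopping-rule values in SAP 8.

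**Assumptions.** 3 survivors per arm score 2 and the rest 0 (20 per arm as a variant); the 0% rate; the 3 against 1 deaths.

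**Formula.** W is the rank sum in the PUL-042 arm (n1 subjects; n2 on placebo; N = n1 + n2), using midranks. E = n1(N+1)/2. Var = (n1·n2/12)·[(N+1) − Σ(t³−t)/(N(N−1))], where t is the size of each tied group. z = (W−E)/√Var.

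**15 v 5 deaths, dropped.** PUL-042 has 82 zeros and 3 twos; placebo has 92 zeros and 3 twos; N = 180. Midranks are 87.5 and 177.5.
- W = 82×87.5 + 3×177.5 = 7707.5; E = 85×181/2 = 7692.5.
- Var = (85×95/12)×(181 − 5268060/32220) ≈ 11774.
- z = 15/108.5 = 0.14, p = 0.89.

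**15 v 5 deaths, ranked worst.** N = 200; tied groups are 174, 6 and 20; midranks are 87.5, 177.5 and 190.5.
- W = 82×87.5 + 3×177.5 + 15×190.5 = 10565; E = 10050.
- Var = (10000/12)×(201 − 5276040/39800) ≈ 57030.
- z = 515/238.8 = 2.16, p = 0.031.

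| Deaths, PUL-042 v placebo | Symptomatic survivors per arm | p, deaths dropped | p, deaths ranked worst | Fisher p on deaths alone |
|---|---|---|---|---|
| 15 v 5 | 3 | 0.89 | 0.031 | 0.032 |
| 15 v 5 | 20 | 0.69 | 0.069 | 0.032 |
| 0 v 5 | 3 | 0.95 | 0.11 | 0.059 |
| 0 v 5 | 20 | 0.86 | 0.31 | 0.059 |
| 3 v 1 | 3 | 0.98 | 0.51 | 0.62 |

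**Reversal.** Assume both arms would have the same 20 symptomatic subjects (total scores 1×5, 2×4, 4×3, 6×3, 8×5), and that the worst 15 die on PUL-042 and the worst 5 on placebo.
- Survivors: 85 on PUL-042, score sum 5, mean 5/85 = 0.06; 95 on placebo, score sum 43, mean 43/95 = 0.45.
- The planned test gives p = 0.026 in favour of the arm with more deaths. With deaths ranked worst, p = 0.79.
- With 4 v 1 deaths in the same setting the values are 0.59 and 0.98.

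**Repeated sampling.** 3,000 simulated trials per scenario, with survivors alike in both arms, 10%, 20% or 40% of them symptomatic, and scores 1 to 6 equally likely. Rejection rates at the 10% level:

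| Mortality, placebo v PUL-042 | Deaths dropped | Deaths ranked worst |
|---|---|---|
| 5% v 5% | 9–10% | 9–11% |
| 5% v 15% | 10–11% | 37–55% |
| 1% v 3% | 10–11% | 12–14% |

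The planned test stays at its nominal level whatever the difference in deaths. The ranked version responds to that difference and keeps its error rate when mortality is equal.

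**The case against.** The strongest reply is that the trial does not lose sight of deaths. Death is score 8 on the primary ordinal scale and also enters the Day 15 severity endpoint. It is assigned an unfavourable value in the ICU and ventilation endpoints, is tested by Fisher's exact method, and has its own interim rule. In the illustration the planned Fisher test gives p = 0.032 for 15 v 5 deaths and 0.059 for 0 v 5, both below the SAP's 10% level. In the second case the ranked symptom test (0.11) is not. Because survivors are set alike, the ranked p-value mainly re-reports mortality. All of this stands. A reader might infer that harm, or a benefit on severe disease, would be hidden in the trial as a whole; the documents do not support that.

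A second reply concerns the inputs. The 5% and 15% rates illustrate a stopping rule and are not forecasts for people who are asymptomatic at enrolment. The 0% rate and the 3 symptomatic survivors are assumptions, and more symptomatic survivors weaken the contrast. This also stands, so the figures show a mechanism and not an expected size.

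Third, a reader might infer that ventilated or ICU subjects also drop out of every later test. No section says they cannot be scored. Fever is graded from recorded temperature, and a living subject may be scored again at a later visit. The established gap is death.

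Finally, ranking death worst on cough or fever changes what the test measures, and observed scores beside a separate mortality result are a defensible alternative. That is a reason to report both. It does not justify leaving the rule unstated when neighbouring endpoints have one.

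**Conclusion.** The point holds for the symptom-score tests only. As written, subjects who have died drop out of all later visit-wise Wilcoxon tests. Those tests then compare survivors, which is inconsistent with the death rules that the same section gives for ICU and ventilation. They can look neutral when deaths differ (0.89 against 0.03 at 15 v 5) and can favour the arm with more deaths if the most symptomatic subjects die (0.026 against 0.79).

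The size depends on the number of deaths, which the documents do not predict for this population, and on the assumed number of symptomatic survivors. With few deaths the effect is small; with none there is no effect from this source. The endpoint is secondary and unadjusted in a study the SAP calls exploratory, and no primary or mortality conclusion changes. It is worth settling before unblinding so that the rule is not chosen after the deaths are known.

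**What to change.** In the Symptom Score part of SAP 6.2:

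1. Give a subject who died on or before the visit the worst rank in each Wilcoxon test.
2. Give the next-worst rank to a living subject only where that score is missing at that visit and the recorded dates show the subject was ventilated or in ICU. Leave other missing scores as missing.
3. Report the observed-scores-only result alongside.
4. Show the numbers scored, dead and missing by arm and visit.

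A rank test needs no invented numeric score. The cost is a few SAP sentences and one extra table. Vital status and the ICU and ventilation dates are already to be recorded, so no new data collection is needed. The downside is that each symptom test becomes a composite with all-cause death. A difference in the ranked result that is absent from the observed-only result should be read as reflecting deaths, or subjects unscored while ventilated or in ICU, and not symptoms among those scored.
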